4.5.4 Imaging

Post-operative CT Scans will be analyzed through 3D reconstruction to report on:

- Placement of the electrode in the cochlea: Scala Tympani versus Scala Vestibuli
- Measurement of modiolar proximity also known as the wrapping factor, scores will range between 0 -1, with 0 being the closest to the modiolus and 1 being furthest on the lateral wall. Wrapping factor will be reported as a percentage.

Possible exploratory analysis may be completed to determine if there is a correlation between the electrode placement and wrapping factor any surgical technique factors as reported on the surgical questionnaire with speech perception (CNC word score and AzBio Sentences in noise).

Electrode position will be also correlated with T& C levels and impedance values after at least 60 days of device use.

4.5.5 Patient Reported Outcomes

Hearing Aid Experience Questionnaire and the Nucleus 7 Questionnaire

These two device use questionnaires were developed by the Sponsor and are used to collect information regarding device usability, subjective preferences, and satisfaction with regards to device use in various listening conditions. The baseline is the Hearing Aid Experience Questionnaire and the follow-up is the N7 questionnaire completed at the 6 month interval. The differences between the N7 questionnaire and baseline (i.e. change in baseline) will be analyzed using a repeated measures, mixed effects model, with the device use difference as the response and variables such as speech perception, age and gender as the explanatory variables. Additionally, the proportion of subjects reporting being satisfied a score of >50 will also be reported.

Speech, Spatial, and Qualities of Speech Questionnaire (SSQ)

The SSQ is a close-ended questionnaire composed of several subjective questions related to quality of speech. The baseline and the follow-up SSQ at the 6 month interval will be recorded for each subject. The differences between the 6-month SSQ and baseline SSQ will be analyzed using a one-sample t-test of the paired difference in pre and post results and performed at the one-sided 0.025 alpha level. If there is significant evidence that the assumptions of the t-test do not hold (i.e. $p < 0.05$ from a Shapiro-Wilks test of normality), a Wilcoxon signed rank test will be used. Additionally, the differences between the 6-month SSQ and baseline SSQ (i.e. change in baseline) may be analyzed using a repeated measures, mixed effects model, with the SSQ difference as the response and variables such as speech perception, age and gender as the explanatory variables. To determine individual postimplant benefit for the categorization system developed by Noble et al. (2009) will be used (≤ 1 = no benefit; $>1-2$ = benefit; $>2-4$ = high benefit; >4 = very high benefit) with the proportion of subjects falling into each category will be reported.

Mini-Tinnitus Questionnaire (Mini TQ)

The Mini TQ is a 12-item questionnaire that defines a general dimension of distress as a result of tinnitus. The Mini TQ will be recorded for each subject at baseline, at six month and 12 months follow-up. The differences between each follow-up Mini TQ and baseline Mini TQ will be analyzed by reporting the proportion of subjects who reported for each of the statements “TRUE”, PARTLY TRUE”, NOT TRUE. Additionally, the differences between each follow-up Mini TQ and baseline Mini TQ (i.e. change in baseline) may be analyzed using a repeated measure, mixed effects model, with the Mini TQ difference as the response and variables such as speech perception, age and gender as the explanatory variables.

Patient Based Resource and Expenditure Questionnaire (PBRE)

The PBRE questionnaire (assessed at baseline, and 6 Months) will be used to collect self-reported costs of hearing loss pre- and post-cochlear implantation. The differences between the 6 month follow-up PBRE and baseline PBRE (i.e. change in baseline) will be analyzed by reporting the proportion of subjects responding on selected questions.

Montreal Cognitive Assessment -MoCA

The MoCA is a rapid screening instrument for mild cognitive dysfunction. It assesses different cognitive domains: attention and concentration, executive functions, memory, language, visuoconstructional skills, conceptual thinking, calculations, and orientation. The baseline and six month follow-up MoCA score will be recorded for each subject. The proportion of subjects who pass (i.e. score 26 or higher) and those who fail a score of below 26 will be reported. Subjects who demonstrate ≥ 2 or ≤ 2 change in their score from baseline to 6-month will be reported as significant if it moves them into or out of a category (i.e. pass versus fail) (Personal communication [name].)

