- A significance level of $\alpha = 0.05$ (two-tailed).
- A desired power of 0.9

Based on these assumptions, a sample size of 26 subjects is required to achieve a power of 90%.

A sample size of 100 adult subjects will be enrolled in the clinical investigation, this large sample will allow for additional analyses to be conducted specifically the additional patient reported outcome measures, where a large sample size is typically desired. Additionally the sample size provides greater justification for generalizability to the wider clinical population.

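### The questionnaire change from Hearing Aid to N7 (and optionally the SSQ change) is assigned a repeated-measures mixed model, but each subject contributes only one difference

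*SAP*

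**What the plan says.** All of the text is in SAP section 4.5.5, Patient Reported Outcomes.

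- **Hearing Aid Experience / Nucleus 7 questionnaires.** The schedule is fixed: "The baseline is the Hearing Aid Experience Questionnaire and the follow-up is the N7 questionnaire completed at the 6 month interval". The change "will be analyzed using a repeated measures, mixed effects model, with the device use difference as the response", with "variables such as speech perception, age and gender as the explanatory variables". This is mandatory. The only other analysis named for this pair is the proportion of satisfied subjects.
- **SSQ.** "The baseline and the follow-up SSQ at the 6 month interval will be recorded for each subject". The planned analysis of change is a "one-sample t-test of the paired difference in pre and post results and performed at the one-sided 0.025 alpha level", with a Wilcoxon signed rank test as fallback. In addition, the change "may be analyzed using a repeated measures, mixed effects model, with the SSQ difference as the response". This second model is optional.
- **Mini TQ.** "The Mini TQ will be recorded for each subject at baseline, at six month and 12 months follow-up". An optional model with almost the same wording is given.

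For none of the three does the section name a random effect, a covariance structure or a within-subject factor such as visit, item, subscale or listening condition.

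**The concern.** A repeated-measures model needs at least two responses per subject. Once the single follow-up score has been subtracted from the single baseline score, one response remains. The same model sentence has been attached to three instruments, and on the stated schedules it fits only the Mini TQ.

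What is at stake is the definition of the analysis. For the device questionnaires this is the only planned analysis of change, with no paired test to fall back on as there is for the SSQ. Section 4.1 justifies enrolling 100 subjects partly by the additional patient-reported outcomes, and section 8.0 commits to reporting the SAP's analyses in full. An analyst who follows the text must either fit a model with a redundant variance parameter or choose a different model once the data are in hand.

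**Working it through.** The SAP gives no sample size, power or estimate for this model, so there is no figure to reproduce. The check is one of identifiability.

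**Inputs from section 4.5.5 (scores and differences per subject)**

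- Hearing Aid / N7: baseline and 6 months, so 2 − 1 = 1 difference.
- SSQ: baseline and 6 months, so 2 − 1 = 1 difference.
- Mini TQ: baseline, 6 and 12 months, so 3 − 1 = 2 differences.

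From section 4.1: "A sample size of 100 adult subjects will be enrolled in the clinical investigation", so the N7 or SSQ model has at most 100 rows for 100 subjects.

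**Algebra**

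Write the change for subject i as d_i = x_i′β + u_i + e_i, with Var(u_i) = σ_u² and Var(e_i) = σ_e². The subject intercept u_i is an assumption, because the SAP names no random effect.

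With one d_i per subject, Var(d) = (σ_u² + σ_e²)·I. The likelihood depends on the two variances only through their sum.

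The generalised least squares estimate is (X′V⁻¹X)⁻¹X′V⁻¹d. When V = c·I, the constant c cancels and leaves (X′X)⁻¹X′d, which is ordinary least squares. The covariate effects are therefore identified, and only the variance split is not.

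**Numerical check**

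This used simulated data for 100 subjects with three subject-level covariates. The effects and a total variance of 2.0 were assumed for illustration. The REML log-likelihood at five splits of the total was:

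| σ_u² / σ_e² | 1 difference per subject | 2 differences per subject |
|---|---|---|
| 0 / 2 | −175.615159 | −349.51 |
| 0.5 / 1.5 | −175.615159 | −341.21 |
| 1 / 1 | −175.615159 | −338.04 |
| 1.5 / 0.5 | −175.615159 | −355.97 |
| 1.9 / 0.1 | −175.615159 | −688.68 |

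With one difference the likelihood is flat. With two it distinguishes between the splits and is highest, of the five, at 1 / 1.

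- **Fixed effects, one difference.** The coefficients were 2.0086, 0.4101, 0.0295 and 0.3863 at every split, identical to ordinary regression.
- **Mixed-model software, one difference.** It reported convergence but warned that the Hessian was not positive definite. It returned a residual variance of 0.9548 and a subject-to-residual variance ratio of 1.0, so the subject variance is 1.0 × 0.9548 = 0.9548. The sum, 0.9548 + 0.9548 = 1.9096, is the ordinary regression residual variance (1.9096). The sum is determined by the data, but the equal split is arbitrary.
- **Mixed-model software, two differences.** There was no warning. The residual variance was 1.0296 and the ratio 0.8364, so the subject variance is 0.8364 × 1.0296 = 0.861.

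**The case against.** The strongest defence is that one row per subject is an inference. The device questionnaires cover several listening conditions, the SSQ has several questions, and the section speaks of differences in the plural. Differences by item, subscale or condition would give several rows per subject, and a site random effect would also be estimable. This stands as a possible intention. But the section makes a single device use difference (and a single SSQ difference) the response, and names no such unit or effect. If one was meant, it has to be stated, so the text needs changing on either reading.

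The defence is right that several stronger conclusions a reader might infer are not supported:

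- **That the whole model is unidentifiable or will not converge.** The covariate effects, which are what the SAP asks for, are identified, and the check above converged with a warning. The SAP plans no report of a within-subject variance component.
- **That leaving out the baseline score biases the result through baseline imbalance.** This is a single-arm study, so there is no treatment contrast to bias. Regressing change with or without the baseline score answers different questions, and the covariate list is open enough to allow it. Adding the score is an improvement, not the repair of an error.
- **That the N7 difference is invalid because it subtracts two different instruments.** Neither questionnaire's items nor its scoring is in the document, so this cannot be judged.

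**Conclusion.** The point holds in a limited form. As written, the mandatory model for the N7-minus-Hearing-Aid difference and the optional model for the SSQ difference have no repeated measure to work on, and their within-subject part cannot be estimated. What can be estimated is an ordinary linear regression of change.

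Severity is minor. The analyses sit in section 4.5, outside the fixed testing sequence of section 4.4. The primary and secondary endpoints, the SSQ paired t-test and benefit categories, and the proportion satisfied are unaffected. The Mini TQ model, with two differences per subject, is estimable.

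The conclusion assumes one score per questionnaire per visit, which is the plain reading of section 4.5.5. It would change only if a within-subject unit that the section does not state had been intended.

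**What to change.** In section 4.5.5:

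1. For the N7 and SSQ changes, replace the repeated-measures mixed model with a linear regression of the 6-month change on speech perception, age and gender, adding the baseline score as a covariate.
2. Alternatively, if differences by item, subscale or listening condition were intended, name that unit and state the random effects or covariance structure.
3. Keep the repeated-measures mixed model only for the Mini TQ, with visit (6 or 12 months) as a factor.

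The cost is a few lines of SAP wording. The baseline scores are already collected, no visit or sample size changes, and the regression is simpler to run than the model it replaces.

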3.0 Subject Population

Study sites will enroll 100 adult cochlear implant candidates at up to 15 North American cochlear implant centers.

Cochlear Americas will adhere to the National Coverage Determination (NCD) for Cochlear Implantation for enrollment of Medicare beneficiaries into the Clinical Evaluation of the Cochlear Nucleus® CI532 Cochlear Implant in Adults. Specifically, the following NCD criteria will be met:

1. Diagnosis of bilateral moderate-to-profound sensorineural hearing impairment with limited benefit from appropriate hearing (or vibrotactile) aids, defined as test scores of less than or equal to 40% correct in the best-aided listening condition on tape-recorded tests of open-set sentence recognition;
2. Cognitive ability to use auditory clues and a willingness to undergo an extended program of rehabilitation;
3. Freedom from middle ear infection, an accessible cochlear lumen that is structurally suited to implantation, and freedom from lesions in the auditory nerve and acoustic areas of the central nervous system;
4. No contraindications to surgery.

Candidates must also meet the following inclusion and exclusion requirements as stated in the study protocol:

Inclusion Criteria:

1. Adults 18 years or older who have a bilateral postlinguistic sensorineural hearing loss.
2. Limited benefit from amplification as defined by test scores of 40% correct or less in the ear to be implanted and 50% or less in the contralateral ear on a recorded monosyllabic word test
 - I. Consistent with the Minimum Speech Test Battery (2011), it is required that all subjects be evaluated at 60 dBA presentation level.
3. Bilateral moderate sloping to profound hearing loss

4. Minimum of 30 days experience with appropriately fit bilateral amplification, fit using the standardized NAL fitting method
5. Proficient in English
6. Ability to complete testing

Exclusion Criteria:

1. Previous cochlear implantation
2. Pre-linguistically deafened (onset of hearing loss at less than two years of age)
3. Ossification or any other cochlear anomaly that might prevent complete insertion of the electrode array
4. Duration of severe to profound hearing loss greater than 20 years
5. Diagnosis of retro-cochlear pathology
6. Diagnosis of auditory neuropathy
7. Unrealistic expectations on the part of the subject regarding the possible benefits, risks, and limitations that are inherent to the surgical procedure and use of the prosthetic device

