4.5.2 Subgroup Analyses

The consistency of the primary endpoint will be examined across subgroups of subjects defined by the following baseline characteristics: age, gender, and duration of hearing loss, baseline CNC word scores, and existing medical comorbidities. Any significant difference between subgroups on endpoints will be explored with additional analyses. Additionally, for the analysis of age subjects will be stratified into 2 groups according to age at time of surgery: 1). <65 years and 2). ≥ 65 years. The effect of age may further be investigated by examining outcomes by decade.

Additional analyses will be completed to evaluate speech perception in quiet and noise at 6 months in the best bilateral listening condition – for most subjects this will be the bimodal condition (CI + contralateral hearing aid), and for others this will be the combined condition CI + Acoustic hearing (same ear) + contralateral hearing aid). Additionally, a subgroup analysis will be done for: Subjects using bimodal hearing and subjects using combined hearing. Differences between and within the subgroup will be evaluated.

Subgroup analysis will be done for: Subjects using hybrid hearing (acoustic + electric in the implanted and subjects using electric alone. Differences between and within the subgroup will be evaluated for primary and secondary endpoints.

The number of subjects falling into each group following surgery cannot be predicted consequently, sample size is not adjusted based on these subgroup analyses.

In addition, the consistency of the primary endpoint will be examined across investigational sites by testing for an effect of site in ANOVA model. Any potential variation between sites in the primary endpoint will be explored by assessing whether or not there are differences in baseline characteristics between subjects at sites that might explain the results.

Exploratory analyses may be conducted to determine factors that predict performance on a CNC word score at 6 months.

Factors that will be considered are:

- Demographic variables such as age, degree of hearing loss, duration of hearing loss
- Other preimplant variables such as: CNC word score, AzBio +10 score, AzBio +5 score, PTA, LFPTA, SSQ score, HUI score and MoCA score (pass/fail)
- Surgical factors, such as surgical approach, speed of insertion of sheath and electrode and number of white markers visible

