5.0 Adverse Event Reporting

An Adverse Event is the development of an untoward medical occurrence or the deterioration of a pre-existing medical condition following or during exposure to an investigational product, whether or not considered causally related to the product or the surgical procedure to implant it. An untoward medical condition can be symptoms (e.g., nausea), signs (e.g., tachycardia, fever) or clinically significant abnormal results of an investigation (e.g., laboratory findings, chest x-ray).

Adverse events that occur during this study may be associated with the implant procedure, including those from general anesthesia, or specifically associated with the use of the device. An adverse event will be considered to be device-related when, in the judgment of the Primary Investigator, there is a logical connection between the use of the device and the occurrence of the event, above and beyond the study procedure itself. Adverse events will be counted regardless of severity, seriousness, onset, duration, or relation to study treatment. A serious adverse event (SAE) is any untoward medical occurrence which:

- Results in death;
- Is life-threatening;
- Requires in-patient hospitalization for > 24 hours or prolongation of hospitalization which is not specifically required by the protocol;
- Results in permanent impairment of a body function or permanent damage to a body structure; or
- Requires medical or surgical intervention to preclude permanent impairment of a body function or permanent damage to a body structure.

For any SAE, if the Primary Investigator judges that there is a logical connection (caused or contributed to) between the use of the device and the occurrence, the SAE will be noted as device-related.

All adverse event rates will be reported as the number and frequency of events with corresponding 95% exact binomial confidence limits, as well as the number of events per patient-time (e.g., events per 10 patient years). These values will be qualitatively compared to the same rates observed in previous cochlear implant studies; no formal statistical comparisons will be conducted.

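### Mini TQ summaries pool subjects with and without baseline tinnitus, so relief and new distress can cancel; a split and a within-subject table would separate them (minor)

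*SAP*

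**What the plan says.** SAP Section 4.5.5 describes the construct: "The Mini TQ is a 12-item questionnaire that defines a general dimension of distress as a result of tinnitus". On collection it says: "The Mini TQ will be recorded for each subject at baseline, at six month and 12 months follow-up".

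Two analyses follow.

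- **Firm:** differences between each follow-up and baseline "will be analyzed by reporting the proportion of subjects who reported for each of the statements", with the response categories TRUE, PARTLY TRUE and NOT TRUE.
- **Optional (worded as something that may be done):** a mixed model of change from baseline "with the Mini TQ difference as the response and variables such as speech perception, age and gender as the explanatory variables".

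Section 3.0 sets entry by hearing loss, for example "Adults 18 years or older who have a bilateral postlinguistic sensorineural hearing loss". Tinnitus appears in neither the inclusion nor the exclusion list. The subgroup factors in Section 4.5.2 are "age, gender, and duration of hearing loss, baseline CNC word scores, and existing medical comorbidities". They are planned for the primary endpoint and do not name tinnitus. The SAP has no scoring rule for a subject without tinnitus, defines no subset with baseline tinnitus, and plans no count of resolved or newly affected subjects.

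**The concern.** A subject with no tinnitus at baseline has no tinnitus distress to relieve. On this scale that subject can stay put or get worse, but cannot improve. A subject with tinnitus can move either way. Because tinnitus is not an entry criterion, the cohort may contain both kinds in unknown proportion, and nothing in Section 4.5.5 separates them.

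This has two consequences for the Mini TQ summaries. First, comparing response proportions between visits shows only the net movement, so relief in some subjects can be offset by new or worsened distress in others. Second, a mean change over all subjects depends on how many had tinnitus to begin with, so it cannot be read as the change a patient with tinnitus might expect. At stake is the interpretation of a supportive patient-reported outcome. No primary or secondary conclusion depends on it.

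**Working it through.** The SAP gives no effect size, power, alpha or sample size for the Mini TQ, so there is no figure to reproduce. The checks below show direction and size under stated assumptions.

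**Inputs**
- N = 100, from Section 4.1: "A sample size of 100 adult subjects will be enrolled in the clinical investigation".
- p, the share of subjects with tinnitus at baseline: not in the SAP; assumed 0.3 to 0.9.
- d and s, the mean and SD of Mini TQ change among subjects with tinnitus: not in the SAP. Only r = |d|/s is needed; assumed 0.3 to 0.8.
- Subjects without tinnitus score at the floor. This is inferred from the construct, since the SAP gives no scoring rule.

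**1. Netting in the firm analysis.** Call a subject affected on a statement if the answer is TRUE or PARTLY TRUE. Change in the affected proportion = (new − resolved)/N.

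| Affected at baseline | Resolved | New | Net change | New among those at risk |
|---|---|---|---|---|
| 60 | 20% × 60 = 12 | 30% × 40 = 12 | 0 points | 30% |
| 80 | 10% × 80 = 8 | 40% × 20 = 8 | 0 points | 40% |
| 70 | 30% × 70 = 21 | 20% × 30 = 6 | −15 points | 20% |

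The first two rows would be tabulated as no change. The third would be tabulated as improvement, with the 6 new cases not visible. All rates are illustrative.

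**2. Mean change, if the optional model is run.** Suppose subjects without tinnitus stay at zero change. The model is simplified here to a test of mean change.
- All-subject mean = p × d, so it shows 30%, 50%, 70% or 90% of the change among subjects with tinnitus at p = 0.3, 0.5, 0.7 or 0.9.
- All-subject variance = p·s² + p(1−p)·d².
- z over all subjects = √N · p · r / √(p + p(1−p)r²).
- z in the tinnitus subset = √(Np) · r.
- Ratio of the two = 1/√(1 + (1−p)r²).

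At p = 0.5 and r = 0.5, z over all subjects = 10 × 0.25/√0.5625 = 3.33, and in the subset √50 × 0.5 = 3.54, a ratio of 0.94. Power is the standard normal probability below z − 1.96.

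| p | r | z ratio | Power, all subjects | Power, subset |
|---|---|---|---|---|
| 0.3 | 0.5 | 0.92 | 71% | 78% |
| 0.5 | 0.5 | 0.94 | 92% | 94% |
| 0.7 | 0.5 | 0.96 | 98% | 99% |
| 0.3 | 0.8 | 0.83 | 95% | 99% |

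Over the assumed grid the ratio runs from 0.83 to 0.996. The size of the estimate changes much more than the strength of evidence, because subjects with zero change lower the variance as well as the mean.

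**The case against.** The strongest case on the other side has five parts.

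- **The mean-change argument concerns an analysis the plan does not commit to.** This stands. The firm analysis is proportions, and the model's covariate list is open-ended, so baseline tinnitus could enter. The netting in step 1, however, applies to the firm analysis.
- **The all-subject summary is a legitimate quantity.** This also stands. Average tinnitus distress across recipients is a proper target, and no distress is a valid lowest value. A reader might infer that subjects without tinnitus lie outside what the instrument can measure, or that the pooled result is meaningless. The SAP supports neither reading. The pooled table answers a population question and leaves the two clinical ones open.
- **New tinnitus is not hidden in the trial.** A reader might infer that it would go undetected. It would not: recording every subject is what makes new distress visible in the data. Section 5.0 also counts newly developed or worsened symptoms: "Adverse events will be counted regardless of severity, seriousness, onset, duration, or relation to study treatment". Section 5.0 does not name tinnitus, and nothing links a rise in Mini TQ to an adverse event, but the definition covers it.
- **The denominator is unclear.** The each-subject wording concerns collection, and the analysis sentence refers to subjects who reported. How subjects without tinnitus complete the form may be in the protocol, which is not at hand. If they left it blank, new cases would lack a baseline and denominators would shift between visits, so a split would still be needed.
- **Selecting on a baseline score above 0 invites regression to the mean** in a single-arm pre/post study. This is correct, and the fix has to allow for it.

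**Conclusion.** The point holds as a minor, inexpensive improvement. As written, the Mini TQ summaries pool subjects with and without baseline tinnitus and can net new or worsened distress against relief, to zero in the worked example. If the optional model is run without a term for baseline status, its mean change is about p times the change among subjects with tinnitus. The SAP does not give p, so the degree of scaling cannot be stated, only shown over a range. Power is little affected: under the normal approximation the largest loss on the assumed grid is about 7 percentage points.

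The conclusion rests on the entry criteria not mentioning tinnitus, the absence of any conditioning in Section 4.5.5, and the inference that a subject without tinnitus scores at the floor. It does not extend to a claim that the trial would miss new tinnitus, or that a test would lose material power. The Mini TQ lies outside the fixed testing sequence of Section 4.4, so the primary and secondary results are untouched.

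**What to change.** Keep recording the Mini TQ in every subject and keep the pooled response table as supportive. In Section 4.5.5 add, at 6 and 12 months:

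- **(a)** A baseline-by-follow-up table, within subject, of responses or score. This alone removes the netting.
- **(b)** Mini TQ change among subjects with tinnitus at baseline. Define the group by reported tinnitus status where that is collected. Otherwise use a baseline Mini TQ above 0, with a stated caveat that selecting on the baseline score exposes the result to regression to the mean.
- **(c)** The proportion of subjects without baseline tinnitus (or with a baseline score of 0) who score above 0 at follow-up. Describe this as new tinnitus distress: a subject may have tinnitus without distress at baseline, and a group starting at 0 can only rise.

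State the number of subjects in each group and how a form from a subject without tinnitus is scored. If the optional model of change is run, include baseline tinnitus status or baseline Mini TQ as a covariate.

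Restricting the analysis to subjects with tinnitus would be the wrong repair, because it discards the information on new distress. The change costs a few sentences of SAP text and one split of data already planned for collection. The drawback is fewer subjects, and so less precision, in each split.

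### The MoCA rule labels a change significant only if it crosses 26, so baseline failers can never be labelled worse, nor passers improved, and no other summary of change is planned

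*SAP*

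**What the plan says.** Everything the SAP plans for change in the MoCA stands in one paragraph of section 4.5.5.

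- Data: "The baseline and six month follow-up MoCA score will be recorded for each subject".
- Group output: "The proportion of subjects who pass (i.e. score 26 or higher) and those who fail a score of below 26 will be reported".
- Individual change, condition on category: a change in score "will be reported as significant if it moves them into or out of a category (i.e. pass versus fail"). The source given is a personal communication.
- Individual change, condition on size: the sentence also sets a threshold of 2 points, which is printed without a minus sign for a fall.

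The MoCA appears once more, in section 4.5.2, as a candidate predictor of the 6-month CNC word score, and there too only as pass or fail. The SAP plans no mean change, no paired comparison and no count of changes within a category. Section 8.0 commits to reporting the analyses that the SAP outlines.

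**The concern.** A rule for individual change should be able to register movement in either direction, whatever the starting score. This one cannot. It joins a size condition to a crossing condition, and the crossing condition settles in advance which direction can count: up for those who start below 26, down for those who start at or above it.

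The subjects with the lowest cognitive scores can therefore appear only as significantly improved or as not significant. In a single-arm pre/post study, a count of improved and worsened subjects built this way partly reflects how many began on each side of 26, not only how much they changed. A reader who sees few worsened subjects could take that as reassurance which the rule cannot give.

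The SAP's other individual-change rules do not work this way. Section 4.3.2 classes CNC and AzBio changes as improvement, no change or decrement, and gives the HUI3 a fixed size of change with no category condition. Section 4.5.5 gives the SSQ a paired test and classes based on the size of change.

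**Working it through.** The SAP states no sample size, power or expected result for this rule, so there is no figure to reproduce. The check is a logical enumeration, followed by a sensitivity range.

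**Inputs from the SAP (section 4.5.5).** Pass is 26 or higher and fail is below 26. The size condition is read as |d| ≥ 2, where d = (6-month score) − (baseline score). A label needs both |d| ≥ 2 and a change of category.

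**Step 1: which directions can be labelled.** Let b be the baseline score and f the 6-month score.

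- If b < 26 and f < b, then f < 26, so there is no crossing. Over all score pairs from 0 to 30, the number of declines from a failing baseline that cross 26 is 0.
- If b ≥ 26 and f > b, then f ≥ 26, so there is no crossing. The number of gains from a passing baseline that cross 26 is 0.

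This needs no assumption about how scores are distributed.

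**Step 2: examples.**

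| Baseline | 6 months | d | Crosses 26? | Labelled significant? |
|---|---|---|---|---|
| 24 | 17 | −7 | no | no |
| 19 | 25 | +6 | no | no |
| 25 | 27 | +2 | yes | yes |

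A change of exactly 2 points crosses only as a gain from 24 or 25, or as a decline from 26 or 27.

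**Step 3: share of changes of 2 or more points that get no label.** This needs the distribution of scores, which the SAP does not give. Assumptions: baseline mean 22, 23, 24, 25, 26 or 27; baseline SD 1.5, 2, 3 or 4; mean change and SD of change (0, 2), (0, 3), (1, 2), (1, 3) or (2, 2). Change is drawn independently of baseline, and scores are rounded and capped at 30. That is 6 × 4 × 5 = 120 scenarios, with 400,000 simulated subjects in each.

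| Scenario (baseline mean, SD; mean change, SD) | Unlabelled share of changes with abs(d) ≥ 2 |
|---|---|
| Lowest: 24, 1.5; +2, 2 | 37% |
| 25, 1.5; +2, 2 | 45% |
| 26, 3; 0, 2 | 66% |
| 25, 4; 0, 2 | 73% |
| Highest: 22, 1.5; 0, 2 | 84% |

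The share exceeds 50% in 112 of the 120 scenarios. In the other 8, baseline scores cluster tightly just below 26 and the mean gain is 1 to 2 points.

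**Step 4: a true decline.** The grid above contains no mean fall, so one was run separately: baseline mean 24, SD 2.5, mean change −1, SD of change 2. About 40% of subjects fall by 2 or more points and about 9% would be labelled. If baseline and follow-up are instead modelled as a true score plus independent error, the 9% becomes about 13%. The exact figure depends on the model; the direction does not.

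**Step 5: the size condition as printed.** "Subjects who demonstrate ≥ 2 or ≤ 2 change in their score from baseline to 6-month" lacks a minus sign. Read literally, every change satisfies it, including 0 and ±1, so only the crossing condition has any effect. A move from 25 to 26 would then be labelled. Across the 120 scenarios, about 3% to 30% of subjects who cross 26 do so on a 1-point change. Restoring the sign removes those but leaves Step 1 unchanged.

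**The case against.** The strongest defence is that the MoCA is described as a rapid screening instrument, for which pass or fail is the natural result. Requiring both a minimum size and a change of category avoids calling small fluctuations significant. Section 4.5.2 uses the MoCA in the same dichotomised way, and the rationale rests on a personal communication that is not available here. This explains why transitions are of interest. It does not explain why a fall of 7 points should be ineligible because the subject started at 24.

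A second defence is that deterioration could be captured as an adverse event under section 5.0, which covers worsening of a pre-existing condition and clinically significant abnormal results. That is possible, but it depends on the investigator's judgement and does not replace a planned summary of the scores.

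Two stronger readings are tempting, and the SAP supports neither.

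- A reader might infer that changes within a category go unreported. The text withholds only the label of significance. It does not forbid showing other changes, and both scores are recorded. What can be said is that no other summary of change is planned.
- A reader might infer that most changes of 2 or more points are missed. That holds under many assumptions but not all. With baseline mean 24, SD 1.5 and a mean gain of 2 (SD of change 2), about 63% of such changes do cross 26.

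Nor is the restriction one-sided against detecting harm: it equally prevents any subject who passes at baseline from being labelled improved.

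**Conclusion.** The point stands as a labelling defect. Under the stated rule, with the size condition corrected, no subject failing at baseline can be labelled worse and no subject passing at baseline can be labelled improved. This follows from the definition alone and is certain. Changes of 2 or more points within a category get no label, and no other planned output shows them.

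The share affected is not fixed by the SAP. It is 37% to 84% over the assumed scenarios and should be quoted only as a range under assumptions.

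Severity is minor. The MoCA is a descriptive measure with no hypothesis test, outside the fixed sequence in section 4.4, so no primary or secondary conclusion depends on it.

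**What to change.** In the MoCA paragraph of section 4.5.5:

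1. State the size condition with its sign: a rise of at least 2 points, or a fall of at least 2 points.
2. Report the proportion of subjects with each, regardless of pass/fail category.
3. Report the mean change from baseline to 6 months with a 95% CI.
4. Show pass/fail transitions in a separate paired 2x2 table (baseline by 6 months), not as a condition for calling a change significant.

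The cost is a wording change and a slightly longer table; both scores are already collected. The downside is that more small changes will be listed. The 2x2 table keeps the screening interpretation that the present rule seems intended to serve.
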